9.5.3. Clinical Laboratory Assessments

A qualified staff member will collect non-fasting samples for clinical laboratory analysis at the times in the visit schedule in Section 7.3. Samples will be sent to a central laboratory for analysis. Refer to the study specific laboratory manual for handling and shipping instructions.

The following tests will be conducted:

Chemistry Panel	Complete Blood Count
Albumin	Hematocrit
Alkaline phosphatase	Hemoglobin
Alanine aminotransferase (ALT)	Platelet count
Aspartate aminotransferase (AST)	Red blood cell morphology
Blood urea nitrogen (BUN)	Red blood cell count
Bicarbonate	White blood cell count
Calcium	White blood cell differential
Chloride	% & absolute
Creatinine	Basophils
Glucose	Eosinophils
Lactate dehydrogenase (LDH)	Lymphocytes
Phosphorus	Monocytes
Potassium	Neutrophils
Sodium	
Total bilirubin	
	Urinalysis

Chemistry Panel	Complete Blood Count
Total protein	
Uric acid	
HDL, LDL, Total cholesterol,	
Triglycerides	

Screening Tests Only

Hep B, HCV, HIV
Quantiferon Gold
Total Iron Binding Capacity (TIBC)
Serum iron
Serum Ferritin
T3/T4, TSH
Serum Pregnancy

The results of the clinical laboratory tests will be reported on the central laboratory's standard reports. The investigator must note NCS or CS to define the clinical relevance of any result that is outside the normal range for the laboratory. The investigator must date and initial every laboratory report.

The investigator or subinvestigator must review all the Screening (Visit 1) laboratory test results against the study entry criteria for each subject prior to Baseline (Visit 2). The investigator must report all laboratory results that are BOTH outside the normal range for the laboratory AND, in the opinion of the investigator, CS as medical history if found prior to the first study medication treatment or as an AE if found after the first study medication treatment begins. The investigator must review all laboratory reports in a timely manner.

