 On Day 29 (Visit 7) subject may be given the option to move into open-label extension treatment. 
 
• If the subject declines the open-label extension, she/he should be seen for the Visit 16 (Post-treatment) assessments 30 days following the date of Day 29 (Visit 7).
 
• If the subject chooses to continue in to the open-label extension, she/he must sign an ICF prior to being dispensed open-label drug and receiving continued study medication application instructions.
 
• If the subject enrolls in open-label treatment after Day 29 (Visit 7), an unscheduled visit will be conducted in order to obtain consent, review drug application instructions, and dispense drug. This will be considered the official date that the subject initiated open-label extension treatment and the scheduling of subsequent visits 8-16 should be based off of this date as referenced by (OLE xxx) in the treatment day schedule header above.
 
											
 Subjects who are eligible and consent to enter the open-label extension will have a baseline CEA and SEA completed at Visit 7 or the unscheduled Visit.											

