## 4. STATISTICAL METHODS

In general summaries will be presented according to double-blind treatment group and additionally for the subset of patients entering open-label. Other than baseline data (ie data collected prior to the first application of double-blind medication), the data summarized corresponds to the period of collection (ie during double-blind or during open-label). For those entering open-label, the open label period begins at the application of open-label medication. Additional details are provided in the data handling and programming specifications document. No imputation of missing data was performed other than completely or partially missing dates as described in the Data Handling and Programming Specifications document.

All Data listings are sorted by double-blind treatment group and patient ID.

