##### **4.4.1 Adverse Events**

Adverse events are coded using the MedDRA dictionary and are categorized by system organ class (SOC) and preferred term (PT). Only treatment emergent adverse events are included in summary tabulations and include the following groupings: Double-Blind ATI-5002, Double-Blind Placebo, Open-Label ATI-5002 and Total ATI-50002 (Double-Blind + Open-Label). All adverse events are included in the data listings including those that are not considered treatment emergent.

To allow differentiation as to which study period an Adverse Event occurred, four categories are defined based upon onset date. Adverse Events that had onset dates prior to the first application of study medication are considered "prior". Adverse events with onset dates on or after the first application of double-blind study medication, prior to entry into open label (first application of open-label study medication) and within 30 days following the last application of study medication are considered "on double-blind therapy" or equivalently "treatment emergent". Events with onset dates on or after the first application of open-label study medication and within 30 days of the last application of study medication are considered "on-open-label therapy" and also considered "treatment emergent". Events with onset dates more than 30 days after the last application of study medication, be it double-blind or open label, are considered as "post-therapy".

Frequency tabulations are presented by MedDRA SOC and preferred term, for all adverse events; study treatment-related, adverse events resulting in discontinuation of study treatment, serious adverse events and adverse events by maximum severity. Adverse events resulting in discontinuation are those with 'action taken' recorded as 'drug withdrawn'.

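### Adverse events dated to Visit 7 are tabulated as open-label ATI-50002 events when open-label drug is first applied that same day, even in vehicle subjects

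*SAP*

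**What the plan says.** SAP 4.4.1 states that "four categories are defined based upon onset date". To be a double-blind event, the onset must fall "prior to entry into open label (first application of open-label study medication"). The open-label category takes "Events with onset dates on or after the first application of open-label study medication". No clock time or visit of collection enters the rule.

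The adverse event columns are "Double-Blind ATI-5002, Double-Blind Placebo, Open-Label ATI-5002 and Total ATI-50002 (Double-Blind + Open-Label"). Open-label events are not split by previous double-blind arm, and every subject in the extension receives ATI-50002.

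SAP section 4 works differently. It allocates post-baseline data to the period in which they were collected, and adds: "For those entering open-label, the open label period begins at the application of open-label medication".

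On timing, footnote 17 of the Schedule of Assessments says: "On Day 29 (Visit 7) subject may be given the option to move into open-label extension treatment". The grid places consent, dispensing and instructions for open-label drug at Visit 7. For later entrants, "If the subject enrolls in open-label treatment after Day 29 (Visit 7), an unscheduled visit will be conducted" and that visit becomes the official start.

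Protocol 9.5.3 requires a clinically significant out-of-range laboratory result to be reported "as an AE if found after the first study medication treatment begins". Protocol 9.5.5 has the equivalent requirement for ECGs.

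**The concern.** Visit 7 ends the randomised period. It has the double-blind physical examination, one of two post-baseline double-blind laboratory draws (Visits 5 and 7), one of two post-baseline double-blind ECGs (Visits 5 and 7), and two of the four double-blind biopsies (PD at Visit 2, PK at Visit 3, both at Visit 7). All of these reflect 28 days of randomised treatment.

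If open-label drug is first applied later the same day, an event dated to Visit 7 shares its date with that application, and the onset-date rule gives the tie to open-label. For a vehicle subject, an abnormality that arose before any ATI-50002 exposure would then be counted against ATI-50002 and be absent from the vehicle column. For an active subject, it would be absent from the randomised active column.

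Safety compared with vehicle is part of the SAP's primary objective. SAP 4.8 records that the planned chi-square test on adverse events was not produced, so these columns are the randomised adverse event comparison.

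**Working it through.** **Step 1: where OLE Day 0 falls.** The schedule header gives study day and OLE day for each open-label column. Study day minus OLE day:

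57−28, 85−56, 113−84, 141−112, 169−140, 196−167, 197−168, 211−182, 281−252, 365−336, 393−364 = 29 in all eleven columns.

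So OLE Day 0 = Day 29 = Visit 7. This fixes the planned scheduling anchor. It does not by itself prove that drug is applied on that day.

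**Step 2: apply the onset-date rule** (double-blind dosing Days 1 to 28):

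| Onset | First open-label application Day 29 | Day 30 | Never |
|---|---|---|---|
| Day 28 | double-blind | double-blind | double-blind |
| Day 29 | **open-label** | double-blind | double-blind |
| Day 30 | open-label | open-label | double-blind |

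For an event dated to Visit 7, the allocation differs only when the first open-label application falls on the Visit 7 date.

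**Step 3: is that case plausible?** Visit 7 samples are due 24 hours (±30 minutes) after a morning application on Day 28, so Visit 7 is a morning visit. Drug for twice-daily use is dispensed there, so a first application later that day would be natural. Neither document fixes it.

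**Step 4: which events are exposed?** SAP section 2 bars extension entry for subjects with clinically significant adverse events or tolerability issues. A clinically significant finding recognised during Visit 7 should therefore keep the subject out, and the event stays double-blind. What remains is:

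- laboratory or ECG findings processed centrally and returned after dispensing, if onset is dated to the sampling day (an assumption, since Protocol 9.5.3 does not define onset);
- minor biopsy-site events that do not bar entry.

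Symptoms reported at Visit 7 with an earlier onset date stay double-blind.

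**Step 5: size per subject.** Randomisation of 12 at 2:1 gives 8 active and 4 vehicle. Take a subject whose only event in the tabulated category is dated to Visit 7:

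- Vehicle subject: Double-Blind Placebo reads 0/4 instead of 1/4, a change of 25 points. Open-Label and Total ATI-50002 each gain one subject, or 1/12 = 8.3 points if all 12 enter the extension (assumption).
- Active subject: Double-Blind ATI-50002 reads 0/8 instead of 1/8, a change of 12.5 points. Total ATI-50002 is unchanged.

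With k such vehicle subjects, the vehicle column understates by k/4 and the Open-Label and Total columns overstate by up to k/12. For k = 1 to 4 that is 25% to 100% and 8.3% to 33.3%. The documents give no basis for choosing k. If the subject has another double-blind event in the category, the double-blind incidence does not change.

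**Step 6: compare with SAP section 4.** Under period of collection, with open-label starting at the application itself, assessments made before that application are double-blind. The same Visit 7 abnormality could then be double-blind in the laboratory or ECG summary and open-label in the adverse event table.

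**The case against.** The case against has real force.

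- **The trigger is conditional.** Dispensing is scheduled at Visit 7 but application is not. Footnote 9 mentions an in-office application on Day 29, but it conflicts with the Day 28 application described elsewhere and cannot settle the matter. Subjects who decline, enter after an administrative gap, or first apply on a later date are unaffected. This stands.
- **The eligibility screen removes the most obvious cases.** This stands, and it leaves only the events listed in step 4.
- **The wording is arguably ambiguous.** The baseline rules in SAP 4.3 and 4.4 refer explicitly to the date of first application, whereas the open-label boundary in 4.4.1 refers to the application. Read with section 4, an event before the application could be called double-blind. But 4.4.1 says its categories rest on onset date, and a date cannot separate events before and after an application on the same day.
- **A tie rule may sit elsewhere.** The SAP refers to a separate data handling and programming specifications document, which was not available. This stands as an uncertainty. The SAP text as written sends ties to open-label.
- **The consequence is small.** There is no formal test of adverse events, and listings are sorted by double-blind arm, so a Day 29 event in a vehicle subject remains visible there. This limits the harm but does not correct the summary tables.

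A reader might infer that the randomised comparison loses its whole end-of-treatment safety assessment. The documents do not support that. Vital signs, chemistry and haematology are summarised by visit, ECG shifts are split by period, and section 4 already places Visit 7 measurements in the double-blind period.

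**Conclusion.** The point holds as a limited misallocation in the adverse event tables. For a subject whose first open-label application falls on the Visit 7 date, SAP 4.4.1 moves an event arising from that day's earlier assessments or biopsies out of the randomised arm and into Open-Label and Total ATI-50002, whichever arm the subject was in. This is inconsistent with the period-of-collection rule in SAP section 4.

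The size is at most 25 points per vehicle subject or 12.5 points per active subject in the double-blind columns, for a subject with no other double-blind event in the category. It rests on a same-day first application, on late-returned findings being dated to the sampling day, and on no tie rule existing in the unseen specifications.

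Two wider readings are tempting and fail. It is not true that every Visit 7 finding is misfiled, because many subjects and most recognised clinically significant findings fall outside the condition. Nor does every misfiled event shift incidence by the full 25 or 12.5 points.

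**What to change.** Amend SAP 4.4.1 so that an adverse event with onset on the date of first open-label application is assigned to the randomised double-blind arm if it arises from a Visit 7 assessment or procedure, or if it is recorded as starting before that application. Other same-date events stay open-label. If the data handling and programming specifications already contain such a rule, bring it into the SAP.

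Confirm also that the period-of-collection rule in SAP section 4 puts Visit 7 data in the double-blind columns of the hepatobiliary and renal tables in SAP 4.4.5, which use the same four groupings.

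The cost is SAP wording and a little programming. Same-date events need a case-by-case check, because the documents describe recording application completion times only for Days 1 and 28, and onset times may not be collected. Few such events are likely in a trial of 12. Events traceable to a Visit 7 procedure need no new data.

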
16. Participation in an investigational drug or device trial in which administration of an investigational study drug or device occurred within 30 days or 5 half-lives (whichever is longer) of Screening (Visit 1). Subjects who have participated in a study of an investigational drug, device or biologic agent for alopecia areata (AA, AU or AT) within 1 year of screening will be eligible to participate only with individual permission from the Medical Monitor.
 
17. Sensitivity to any of the ingredients in the study medications.
 
18. History of or current alcohol or drug abuse within 2 years of assessment for study enrollment.
 
19. Screening ECG findings of:
 
 • QTcF >450msec for males or >470msec for females (use of the ECG algorithm is acceptable for this purpose) • Heart rate < 45 or > 100 beats/minutes (inclusive) • Rhythm disturbance other than sinus arrhythmia or ectopic supraventricular rhythm (ectopic atrial rhythm) • Conduction disturbance including PR >240msec, pre-excitation (delta wave and PR <120msec), second degree or higher AV block • Acute or chronic signs of ischemia • Left Bundle Branch Block • Prior myocardial infarction 		

Duration of Treatment
 
Double-blind Treatment
 
Screening period up to 30 days.
 
Double-blind treatment period is 29 days (maximum of 28 days of study medication application).
 
Post-treatment Visit 16 is up to 33 days (30 +3 days) following Day 29 for subjects not continuing into the open-label extension.
 
Total study participation for subjects from Baseline (Visit 2) through Post-treatment Visit 16(Day 59 + 3 days) is up to 62 days (29 + 33).
 
Double-Blind + Open-Label Extension
 
The duration of the total study participation from Baseline (Visit 2) to Week 56 (Visit 16) is anticipated to be a maximum of 400 days (393 + 7 days).
 
The duration of the open-label extension (OLE) should be based on the date of the visit that the subject initiated OLE treatment rather than the days from Baseline (Visit 2). For subjects who entered the open-label extension and had a gap between Visit 7 and entry into the open-label extension due to an administrative delay total study participation may be longer than 400 days.
		

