 UPT must be performed prior to randomization at Visit 2 and prior to study medication application at Day 28 (Visit 6) and at each OLE visit. UPT must be negative for the subject to continue in the study. WOCBP must have a negative serum pregnancy test at screening and a negative UPT at baseline prior to randomization.											
 SALT is performed prior to ALODEX score using device provided.											
 ALODEX is performed after SALT score using device provided.											
 Photography should be performed on Day 1 (prior to application of study medication application) and on Day 29 & Day 197 prior to the scalp biopsy.											
 Subjects must be instructed to apply the study medication according to the instructions in Appendix 1. Subjects will apply the first dose of study medication on the morning of Day 1 (Visit 2) and the last application of study medication on the morning of Day 28 (Visit 6), under the instruction and supervision of the study staff. Study medication at these visits should be applied in the morning to allow the 8-hour post dose assessments to occur at a reasonable time. On Day 1 (Visit 2) and Day 29 (Visit 7) subjects will only apply study medication once-a-day in the office.											
 PK: A 4mm punch biopsy must be obtained on Day 2 (Visit 3) and Day 29 (Visit 7) 24 hours (± 30 minutes) after study medication application on Day 1 (Visit 2) and Day 28 (Visit 6).											
 PD: A 4mm punch biopsy must be obtained on Day 1 (Visit 2) before application of first dose of study medication and Day 29 (Visit 7) 24 hours (± 30 minutes) after study medication application. Subjects that choose to continue in to open-label extension treatment will also have a 4mm punch biopsy collected on Day 197 (Visit 13).											

	Open-Label Treatment										Post-Treatment  Visit 16
	Visit 8	Visit 9	Visit 10	Visit 11	Visit 12	Call	Visit 13	Optional Visit (Suture Removal)	Visit 14	Visit 15	
Week	8	12	16	20	24	28	28	30	40	52	56
Treatment Day	57 (OLE 28)	85 (OLE 56)	113 (OLE 84)	141 (OLE 112)	169 (OLE 140)	196 (OLE 167)	197 (OLE 168)	211 (OLE 182)	281 (OLE 252)	365 (OLE 336)	59/ 393 (OLE 364)
Treatment Window(days)	± 3	± 3	± 3	± 3	± 3	± 3	± 3	± 3	± 7	+7	± 3/± 7

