#### **4.4.4 ECG assessments**

The core laboratory's interpretation of the ECGs are summarized as "shift" from baseline to "worst" overall interpretation recorded after baseline where the order of severity of the interpretations from best to worst are "Normal", "Abnormal, NCS" and "Abnormal, CS". Separate summaries are used for post baseline data collected during double-blind and during open-label. If applicable, follow-up visits are included in the post-baseline data dependent upon entry into open-label (ie included in double-blind assessment if a patient did not enter open-label and in open-label assessment if they did).

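### For subjects who do not enter the extension, the SAP's 30-day treatment-emergent window can close one day before the scheduled post-treatment visit, so adverse events with onset on that visit day are left out of the AE tables

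*SAP*

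**What the plan says.** SAP 4.4.1 assigns each adverse event to a period by its onset: "four categories are defined based upon onset date". Onset up to 30 days after the last application, and before any open-label application, is treatment emergent on double-blind therapy. The post-therapy category takes "Events with onset dates more than 30 days after the last application of study medication, be it double-blind or open label". For the tables the rule is "Only treatment emergent adverse events are included in summary tabulations". For the listings it is "All adverse events are included in the data listings including those that are not considered treatment emergent".

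Footnote 9 of the schedule of assessments places "the last application of study medication on the morning of Day 28 (Visit 6".

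The documents time Visit 16, for subjects who stay out of the extension, in two ways:

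- **Counted from Day 29.** Footnote 17 says of a subject who declines that "she/he should be seen for the Visit 16 (Post-treatment) assessments 30 days following the date of Day 29 (Visit 7". The synopsis, under duration of treatment, says "Post-treatment Visit 16 is up to 33 days (30 +3 days) following Day 29 for subjects not continuing into the open-label extension". The schedule header shows Day 59 with a window of ± 3 days.
- **Counted from Day 28.** The synopsis design text, Protocol 7.1 and SAP 2 count 30 days from Visit 6. Protocol 7.1 and SAP 2 add ± 3 days.

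On follow-up ECGs, SAP 4.4.4 says they are "included in double-blind assessment if a patient did not enter open-label and in open-label assessment if they did".

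**The concern.** Safety is part of the primary objective. Protocol 10.1.4 collects adverse events to the end of the last visit, but the SAP window can end the day before that visit.

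Visit 16 includes laboratory tests, an ECG and vital signs. Protocol 9.5.1, 9.5.3 and 9.5.5 require clinically significant abnormal results after first application to be reported as adverse events, and such findings are naturally dated to the day of the test. For subjects outside the extension, this is the only scheduled laboratory test and ECG after Visit 7. These subjects include anyone kept out because of clinically significant adverse events or tolerability problems.

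One abnormal ECG at this visit could therefore appear in the double-blind ECG shift table and in no AE table. Whether the event is tabulated would turn on a one-day difference between two passages and on the day the visit was booked.

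**Working it through.** This is study-day arithmetic.

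**Inputs**
- Last double-blind application: Day 28 (footnote 9).
- Treatment-emergent limit: 30 days after the last application (SAP 4.4.1).
- Visit 16 without the extension: 30 days after Day 29, or 30 days after Day 28; window ± 3 days.
- Extension: Visit 15 at OLE Day 336 (+7), Visit 16 at OLE Day 364 (± 7).

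**The plan's own figures.** 29 + 30 = Day 59, and 29 + 33 = 62 days. Both match the synopsis.

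**Last tabulated onset day.** 28 + 30 = Day 58.

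**Gap from last application to Visit 16** (visit day − 28)

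| Anchor | Nominal day | Nominal gap | Range of gap | Permitted visit days beyond 30 days |
|---|---|---|---|---|
| Day 29 | 59 | 31 | 28 to 34 | 4 of 7 (Days 59–62) |
| Day 28 | 58 | 30 | 27 to 33 | 3 of 7 (Days 59–61) |

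The last column counts visit days. It is not a share of adverse events.

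**Onset days affected.** The rule uses onset date, so the relevant count is onset days from Visit 7 (Day 29) to Visit 16.
- Visit on Day 59: 59 − 29 + 1 = 31 onset days. Days 29–58 (30 days) are tabulated and Day 59 is not: 1/31 = 3%.
- Visit on Day 62: 62 − 29 + 1 = 34 onset days. Days 59–62 (4 days) are not tabulated: 4/34 = 12%.

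**Extension.** The documents do not fix one day for the last open-label application.
- Last application at OLE Day 336: Visit 16 (OLE 357–371) falls 21 to 35 days later. The nominal gap is 364 − 336 = 28 days, inside the limit. Five of the 15 permitted days (gaps 31–35) are outside.
- Last application at OLE Day 343 (Visit 15 at +7): the gap is 14 to 28 days, and none is outside.
- Application for the full 52 weeks: 52 × 7 = OLE Day 364, the nominal day of Visit 16, and none is outside.

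**Weight of one subject.** With the planned 8 active and 4 vehicle subjects, one subject is 1/8 = 12.5 or 1/4 = 25 percentage points of an arm. An incidence moves by that much only if the omitted event is the subject's sole event in the row concerned.

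**The case against.** A reader might infer that whatever an on-time follow-up visit finds drops out of every AE table. The documents do not support that. SAP 4.4.1 classifies by onset, not detection, and Protocol 10.2.1 elicits events by asking about changes since the previous visit. An event reported on Day 59 with onset on any of Days 29–58 is tabulated.

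Other points against the concern:

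- **The Day 28 anchor.** On the synopsis design text, Protocol 7.1 and SAP 2, the nominal visit is at 30 days, inside the window. This stands. Only visits one to three days late are then affected, and the documents do not say which anchor governs. Footnote 9 also mentions an in-office application on Day 29, against its own Day 28 statement; that would make the gap 59 − 29 = 30 days.
- **The data are shown elsewhere.** The follow-up ECG enters the shift table, SAP 4.4.5 tabulates the worst post-baseline laboratory value, SAP 4.4.3 summarizes vital signs by visit, and every event is listed. With 12 subjects the listings can be read in full. This stands. What is lost is the event's place in the AE tables.
- **Physical examination.** The schedule marks one at Visit 16 without distinction, but Protocol 9.5.2 requires it there only for extension subjects. It should not be counted among the affected findings.
- **Overall incidence.** Subjects kept out of the extension because of adverse events already count as having an event, so a further omitted event would not change their contribution to overall incidence. This stands, though rows for individual terms could still change.
- **A fixed window gives everyone the same risk period.** This is a fair reason not to end the window at each subject's visit date. A longer common cut-off meets it.

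**Conclusion.** The concern holds in a limited form. For subjects outside the extension, with a Day 28 last application and Visit 16 timed by the schedule, footnote 17 and the synopsis duration text, adverse events with onset on the day of a Day 59–62 visit are classed post-therapy and left out of the AE summary tables. They remain in the listings. The treatment of the same visit differs between SAP 4.4.1 and SAP 4.4.4, and the SAP gives no reason.

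The size is small: one onset day in 31 for a visit on the scheduled day, and four in 34 at the latest permitted day. Under the Day 28 anchor, only visits one to three days late are affected. In the extension, the problem arises only if the last application is near OLE Day 336 and Visit 16 falls more than 30 days later.

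The documents do not give the number of subjects who stay out of the extension or the rate of visit-day findings, so no expected number of omitted events can be stated. The case for change rests on the inconsistency in primary-objective safety data and the low cost of removing it.

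**What to change.** In SAP 4.4.1, extend the treatment-emergent window so that it includes the post-treatment visit, ending at the first open-label application for double-blind events in subjects who enter the extension. There are two ways to do this:

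1. End the window at the later of 30 days after the last application and the date of Visit 16.
2. Use a common cut-off that covers the latest in-window visit: 62 − 28 = 34 days without the extension and 371 − 336 = 35 days with it. The first figure assumes a Day 28 last application, the second a last application at OLE Day 336.

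Also reconcile the Day 28 and Day 29 anchors for Visit 16 across the synopsis, Protocol 7.1, SAP 2 and footnote 17, and the two application days named in footnote 9.

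The cost is one sentence in the SAP and one derivation line, with no new data. Slightly more events may be counted. With the first option the risk period varies by a few days between subjects; the second avoids this. SAP 4.6 reports that an unblinded PK review of the first six patients has taken place, so the change should be recorded, with its date and reason, in SAP 4.8.
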